#### 4.7 Hypothesis framework

PROSPER II is a superiority trial comparing glasses wear to non-wear. Analysis of the trial will entail calculation of treatment effect measures and confidence intervals to assess the difference between the two arms. Results from the statistical analysis will generally be presented by two-sided confidence intervals (CIs) with a confidence level of 95%. Superiority will be claimed if the two-sided p-value is less than 5% and the treatment estimate favours the use of glasses. If the lower limit is above 0, superiority of glasses-wear against non-wear can be concluded.

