#### 4.8 Sample size & power

The primary outcome is efficiency, defined as the number of items completed divided by target number of items per unit time as defined by industry standards. Efficiency is thus a

dimensionless ratio. We will top code the efficiency at 99th percentile to account for outliers. This outcome will be compared between the two study groups. An increase in mean efficiency of 0.0425 in the intervention group compared to the control group (the latter having a baseline mean of 0.53 per day and SD 0.19, based on Shahi records) is deemed economically meaningful to Shahi. Effects of this size have been detectable in other trials in this setting. With a two-sided significance level of  $p=0.05$ , power of 90% and a serial correlation in outcomes of 0.8 (data from previous Shahi trials), our sample size calculation yields a required sample size of 152 subjects per group. Allowing for 80% adherence and 10% loss to follow-up each month, we calculated that a sample size of 500 individuals (250 per group) is required.

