### 8.3 Losses to follow-up

Missing data due to loss to follow-up is likely to be linked to staff turnover. Worker turnover at Shahi is accounted for in the sample size calculation and, based on historical data, is not expected to exceed 10% per month.

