## 9. COMPARATIVE ANALYSES

### 9.1 Analysis of primary and secondary outcomes

The primary endpoint is difference in efficiency during the 3 months of intervention between the treatment and control groups. The objective is to show that glasses-wear is superior to non-wear in improving worker efficiency. The null-hypothesis will be rejected on a 5% level if the two-sided 95% CI of the treatment full analysis set difference  $\mu_{\text{glasses}} - \mu_{\text{non-glasses}}$  excludes 0. If the lower limit is above 0, superiority of glasses wear against non-wear can be concluded. The hypothesis will be tested using an analysis of covariance (ANCOVA) model. In the regression specification, the outcome variable will be daily mean efficiency for each participant per day. The factors, covariates and interaction terms in the ANCOVA model are listed in the table below.

Factors and covariates at baseline	Type	Categories
Randomised treatment	Factors	Intervention, Control
Sex	Factors	Male, Female
Skill grade	Factors	<median, $\geq$ median
Factory type	Factors	Urban, rural
Spectacle wear compliance	Factors	<median, $\geq$ median
Age	Covariate	Not applicable
Baseline efficiency	Covariate	Not applicable

The factors and covariates will be included in the model as main effects in an additive structure. The estimated treatment difference between glasses-wear and non-wear will be reported together with the associated two-sided 95% CI and corresponding p-value. The standard errors will be clustered at the individual participant level.

Linear regression analyses will be performed on potential determinants of primary and secondary outcomes. The study group and all significant variables with p values less than 0.20 in simple regression analyses will be included in multiple regression models. Histograms, normal quantile plots (QQ Plot), and the Shapiro-Wilk normality test will be used to test the normality assumption in regression models. For the APEDS VFQ tool, a composite score (16 items) will be created on 0-100 scales, with higher scores indicating better results. Intervention costs will comprise the screening test, glasses (and any replacement thereof) as well as direct and indirect costs to the company for facilitating workplace-based sight tests. We will report cost effectiveness distinguishing between study costs and program costs. The cost effectiveness analysis will include both the costs to identify presbyopia and treat presbyopia.

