The analysis of primary and secondary outcomes will be adjusted for the minimisation factors (age, work tenure at the textile factory, efficiency during baseline assessment) to account for the correlation between treatment groups introduced by balancing the randomisation. The analysis will incorporate adjustment for glasses wear adherence to

account for any potential confounding effect on the productivity measures. Adherence to wearing glasses will be considered a covariate in the regression models assessing primary and secondary outcomes. Both the crude unadjusted and adjusted estimates will be presented, but the primary inference will be based on the adjusted analysis.

For multiple imputation of missing data in assessing primary outcomes we will create 20 copies of the data, in which missing values shall be imputed by chained equations, and the datasets will be averaged.

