## **9.4 Procedure for accounting for missing, unused, and spurious data**

Missing data will be described, for example, by presenting the number and percentage of individuals in the missing category. All data collected on data collection forms will be used, since only essential data items will be collected.

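### Averaging the 20 imputed datasets understates the primary standard error; the plan should pool estimates and variances instead

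*SAP*

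**What the plan says.** SAP section 9.1 sets the rule for missing data in the primary outcome. Of the 20 copies to be created, it says: "missing values shall be imputed by chained equations, and the datasets will be averaged". Section 9.1 of the Combined protocol and SAP repeats it word for word. Section 9.4, whose title covers missing data, deals only with reporting: "Missing data will be described, for example, by presenting the number and percentage of individuals in the missing category". Neither document says that the model is fitted in each copy, that the results are pooled, or that between-imputation variance is added.

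The analysis this feeds is an ANCOVA in which "the outcome variable will be daily mean efficiency for each participant per day", with standard errors clustered by participant. On the decision rule, section 9.1 says "The null-hypothesis will be rejected on a 5% level" when the two-sided 95% confidence interval excludes zero. Section 4.7 adds: "Superiority will be claimed if the two-sided p-value is less than 5% and the treatment estimate favours the use of glasses".

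Missing outcomes are expected. The sample size in section 4.8 is set "Allowing for 80% adherence and 10% loss to follow-up each month", and section 8.3 says that worker turnover "is not expected to exceed 10% per month".

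**The concern.** The sentence averages the datasets, not the estimates. A mean over 20 completed copies is a single dataset whose imputed values have lost nearly all their random component. An ANCOVA on it treats predictions as observations. The spread between copies, which is the reason for creating several, never reaches the standard error.

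At stake is the validity of the primary test. If the standard error is too small, the interval is too narrow and superiority is claimed more often than the stated 5% rule allows. Clustering by participant does not repair this for a worker with no follow-up data. For a worker who leaves part-way, it limits the damage, because the imputations then carry that worker's own earlier values.

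**Working it through.** **Inputs from the SAP.** 250 per group, SD 0.19, correlation 0.8, difference 0.0425, 90% power and two-sided 5% (section 4.8); loss of up to 10% per month (sections 4.8 and 8.3); 20 imputations, repeated daily outcome and participant-clustered standard errors (section 9.1).

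**Not in the documents, so assumed.** When workers leave, whether leaving relates to outcome, how correlation falls with time, which rows after departure are imputed, and what enters the imputation model.

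**Step 1: the plan's own figure.** n = 2 × [SD × (z0.975 + z0.90) / difference]² × (1 − r²) = 2 × [0.19 × (1.960 + 1.282) / 0.0425]² × (1 − 0.64) = 151.2, rounded up to 152 per group. This matches section 4.8, so SD 0.19 and correlation 0.8 are used below.

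**Step 2: expected loss at the ceiling.** Workers gone by month 3: 1 − 0.9³ = 27.1%. At a steady rate, person-time lost: 1 − 0.271 / (3 × 0.1054) = 14.3%. At 5% per month, workers gone: 1 − 0.95³ = 14.3%.

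**Step 3: what averaging does.** The ANCOVA coefficient is linear in the outcome. With complete covariates, the averaged dataset therefore gives the same point estimate as the mean of the 20 estimates. The variance is different: the averaged data have artificially small residuals where values were imputed, and the between-imputation term is absent.

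**Step 4: closed form, one outcome per worker.** With a fraction m missing, the residual sum of squares shrinks by about (1 − m) while the nominal sample size stays full. The true variance corresponds to a sample of (1 − m) × N. So reported SE / true SE is about 1 − m, and type I error is about 2 × [1 − Φ(1.96 × (1 − m))].
- m = 0.143: ratio 0.857, type I error 9.3%.
- m = 0.271: ratio 0.729, type I error 15.3%.

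**Step 5: simulation of the repeated-measures design under no effect.** 10,000 replicates per scenario (Monte Carlo error 0.2 to 0.4 points). Twelve weekly rows stood in for daily rows, leaving was unrelated to outcome, and every row after departure was imputed. Imputation was sequential, proper and normal, on arm, baseline and earlier weeks. The analysis was ANCOVA on arm and baseline with participant-clustered SE. Correlation was either constant at 0.8 or decaying (between weeks 0.55 + 0.40 × exp(−lag/4); baseline to follow-up from 0.80 down to 0.58). Results at 10% loss per month, averaged dataset:

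| When workers leave | Type I error, constant | Type I error, decaying | Mean SE / true SD, constant |
|---|---|---|---|
| Start of each month | 8.8% | 9.5% | 0.00672 / 0.00771 = 0.87 |
| Spread by week from day one | 6.7% | 8.0% | 0.00691 / 0.00745 = 0.93 |
| Spread by week after a first week | 5.7% | 7.0% | 0.00700 / 0.00728 = 0.96 |
| Month end | 5.4% | 6.2% | 0.00707 / 0.00724 = 0.98 |
| All leavers lack any follow-up outcome | 16.4% | 16.1% | 0.00614 / 0.00862 = 0.71 |

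At 5% per month with earlier records kept, the range was 5.3% to 7.5%. Rubin's rules on the same data gave 4.6% to 5.5% in all 20 scenarios.

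**Step 6: repeat with separately written simulations.** Imputing from the worker's own earlier periods, averaging gave 5.7% to 8.3% and Rubin's rules 5.0% to 6.1%. With leavers wholly missing the figures were 16.5% and 5.7% (Monte Carlo error about 0.4 to 1.0 points). A further run of 2,000 replicates per scenario gave 6.9% (weekly leaving), 8.2% (start of month) and 14.6% (wholly missing) for averaging, against 5.3%, 4.7% and 4.4% for Rubin's rules.

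**Step 7: does pooling alone suffice?** If the imputation model uses only baseline and arm, and so ignores that rows belong to the same worker, averaging gave 8.9% to 10.2% and Rubin's rules still gave 7.7% to 9.2%. The further run gave 10.3% and 8.9%. In that case most of the excess comes from the imputation model.

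**The case against.** The best defence is that the sentence is loose wording. It speaks of multiple imputation, 20 copies and chained equations, and copies have little purpose if they are collapsed before analysis. That is plausible. But section 2 of the SAP presents the plan as the rules to be followed, and nothing else in it supplies the standard procedure. Even averaging the 20 estimates and their standard errors would omit the between-imputation variance.

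Other points stand in part:
- The documents do not say outright that the imputed analysis supplies the deciding interval. That is inferred from the sentence's reference to the primary outcome and from the intention-to-treat strategy in section 7.1.
- The rates above are two-sided. Section 4.7 also requires the estimate to favour glasses, so by symmetry the rate of false superiority claims is about half: 2.7% to 4.8% against 2.5%, at 10% loss with earlier records kept.
- The upper figures need workers to leave at the start of a month, and 10% is a ceiling.
- The simulated model omits sex, skill grade, factory type, age, tenure and spectacle-wear compliance, all of which the plan would adjust for. The percentages illustrate the error; they are not the exact error rate of the planned test.
- As step 7 shows, pooling alone may not restore 5%.

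None of these changes the direction of the error. The last one enlarges the fix.

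**Conclusion.** The concern holds: the combination rule is wrong as written, in both documents. Applied literally, it gives too small a primary standard error and an anti-conservative test. With leavers' earlier records used and loss at the 10% monthly ceiling, the standard error is 2% to 16% too small across both correlation structures, and two-sided type I error is about 5% to 10%. It reaches about 16% only if every leaver lacks any follow-up outcome.

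Confidence is high on the wording and the direction. It is moderate on the size, which depends on departure timing, actual loss, correlation between days, the rows imputed and the simplified model. The plan should be corrected before analysis. If the authors confirm that they meant pooling, the correction is one of wording only.

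**What to change.** In SAP section 9.1, replace the averaging clause with text such as:

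> *The primary ANCOVA with participant-clustered standard errors will be fitted in each of the 20 imputed datasets, and the estimates and variances will be combined by Rubin's rules (mi estimate in Stata).*

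Adopt with it a statement of the imputation model: the variables (arm, baseline efficiency, stratification factors and the worker's own earlier observed efficiency), the level of imputation (day or participant), how the within-worker correlation is handled, and which days after departure are imputed. State also that this analysis supplies the primary interval, if that is intended. The same sentence in the Combined protocol and SAP should be corrected if that document remains in force.

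The cost is a few sentences, with no change to data collection or sample size. At 10% monthly loss with earlier records kept, the pooled standard error was about 2% to 18% larger than the averaged-data one (4% to 12% when leaving is spread by week), so the interval widens modestly.

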## **9.2 Pre-specified subgroup analysis**

The consistency of the effect of the intervention across specific subgroups will be assessed using the statistical test of interaction. Pre-specified subgroup analyses include:

- Sex
- Skill grade (<median,  $\geq$ median)
- Reading glass power (low, reading glasses powers < 1.25D; moderate, 1.25D  $\leq$  reading glasses powers < 2.00D; high, reading glasses powers  $\geq$ 2.00D)
- Age group (35 to 39 years, 40 to 49 years, 50 years and older)
- Compliance rate observed in the factory (<median,  $\geq$ median)
- Presenting binocular near visual acuity of N8 and worse

Subgroup analysis will be performed on the primary outcome.

## **9.3 Significance levels and adjustment of p-values for multiplicity**

For the primary outcome, including subgroup analyses, a 95% confidence interval will be calculated. 99% confidence intervals will be used for the secondary outcomes, to take account of the number of comparisons.

## **9.4 Procedure for accounting for missing, unused, and spurious data**

Missing data will be described, for example, by presenting the number and percentage of individuals in the missing category. All data collected on data collection forms will be used, since only essential data items will be collected.

## **9.5 Exclusion of data**

Before data are locked for statistical analysis, a blinded review of all data will take place. Any decision to exclude a subject or single observation from the statistical analysis is the joint responsibility of the PROSPER II trial statistician, the international trial manager and the Chief Investigator. Exclusion of data from analyses will be used restrictively and normally no data should be excluded from the full analysis set. The subjects or observations to be excluded, and the reasons for their exclusion will be documented and signed by those responsible before database lock. The subjects and observations excluded from analysis sets, and the reason for this, will be described in the clinical trial report. Any observation excluded from the analysis database will be documented before database lock with the reason for exclusion provided.

## **9.6 Statistical software employed**

Stata, version 18

## **10. SAFETY DATA ANALYSIS**

### **10.1 Serious adverse events**

Serious adverse events will be listed by allocation as well as allocation received.

## **11. ADDITIONAL EXPLORATORY ANALYSIS**

Any analyses not specified in the analysis protocol will be exploratory in nature and a 2-sided significance level of 0.01 will be used with 99% confidence intervals.

## **12. DEVIATION FROM ANALYSIS DESCRIBED IN PROTOCOL**

None at present

## DOCUMENT HISTORY

Version	Date	Edited by	Comments	Timing in relation to unblinding
1.0	TBD	GM	Approved by signatories, updated to version 1.0	Prior to trial registration

## 2. INTRODUCTION

This document details the proposed presentation and analyses for the main analysis reporting results from the USAID and Clearly funded randomised controlled trial PROSPER II (PROductivity Study of Presbyopia Elimination among aRtisans: a randomised trial on the effect of providing near glasses on the productivity of Indian textile workers). The results reported in this publication will follow the strategy set out here. Subsequent analyses of a more exploratory nature will not be bound by this strategy, although they are expected to follow the broad principles described. The principles are not intended to curtail exploratory analysis (for example, to decide cut- points for categorisation of continuous variables), nor to prohibit accepted practices (for example, data transformation prior to analysis), but they are intended to establish the rules that will be followed, as closely as possible, when analysing and reporting the trial.

The analysis plan will be available on request when the principal manuscripts are submitted for publication. Suggestions for subsequent analyses by journal editors or referees will be considered carefully and carried out, as far as possible, in line with the principles of this analysis plan.

Any deviations from the statistical analysis plan will be described and the rationale given in the final report of the trial. The analysis will be carried out by an identified, appropriately qualified and experienced statistician, who will ensure the integrity of the data during processing. Examples of such procedures include quality control and evaluation procedures.

## 4. BACKGROUND INFORMATION

### 4.1 Rationale

PROSPER II is a randomised controlled trial (RCT) assessing the effect of reading glasses on the productivity of presbyopic textile workers in Bangalore, India.

### 4.2 Objectives of the trial

Globally, 2.7 billion people do not have the eyeglasses they need to earn, learn, travel safely in traffic and participate in civic life. Among these, 1.1 billion people lack a simple pair of reading glasses to correct impaired near vision, called presbyopia. Presbyopia, the essentially universal decline in unaided near vision that occurs with aging, is the world's most common cause of vision impairment. Loss of accommodation (ability to change focus from distance to near) due to presbyopia can begin as early as age 30 years, commonly becomes functionally apparent by 40, and is essentially complete by 55, meaning that presbyopia is most common at the height of the working years. Few trials have been published which address the question of whether healthcare interventions can improve work performance as well as workplace retention, especially among persons over the age of 40 in low and middle-income countries (LMICs). We propose to carry out a randomized trial measuring the effect of presbyopic correction on productivity in Indian textile workers in the Bangalore area.

PROSPER II will assess the impact of free reading glasses on productivity for workers in textile factories in Bangalore, India. We hypothesise that the change in worker efficiency over the 3-month evaluation period will be greater in the Intervention compared to the Control group, adjusting for baseline efficiency.

### **4.3 Trial design**

PROSPER II is an investigator-masked, multi-center randomized controlled trial.

### **4.4 Eligibility**

#### **4.4.1 Inclusion criteria**

Shahi employees will be eligible to participate if:

- they are aged 30 years or older
- have an unaided distance visual acuity of 6/12 or better in both eyes
- have presbyopia, defined as the inability—correctable with reading glasses—to read the N8 line using both eyes together, on a tumbling E near vision chart at 40cm
- have worked in the sewing department for 3 months or more

#### **4.4.2 Exclusion criteria**

Shahi employees will be ineligible to participate if:

- they own reading or distance glasses (regardless of accuracy)
- have ocular pathology in either eye detected during the eye examination, or history of such disease based on self-report
- have a low likelihood of completing follow-up in the study due to current plans to move out of the area or leave employment at Shahi during the follow-up period

### **4.5 Interventions**

Eligible participants will be randomly assigned to Intervention and Control Groups (1:1). Intervention group participants will receive free reading glasses within a week of

undergoing a vision screening at the factory. Control group participants will receive reading glasses at the end of the assessment period (three months after vision screening). The trial will be investigator-masked, but not participant-masked, because the investigators do not feel provision of zero-power glasses to the control group is ethical. However, participants will have limited knowledge of the study hypothesis, limiting potential placebo effects.

#### **4.6 Definition of primary and secondary outcomes**

##### **4.6.1 Primary outcome**

The primary outcome for sew-ers enrolled in the study is efficiency, defined as the number of items completed divided by target number of items per unit time (as defined by industry standards). Daily mean efficiency for each participant will be assessed from trial entry to closure as recorded in Shahi's Manufacturing Execution System software (SIPMONlite).

##### **4.6.2 Secondary outcomes**

The secondary outcomes are:

- changes in skill grade and associated change in wage
- adherence with spectacle wear
- worker self-reported self-efficacy
- Quality of Life using the THRIVE Near Vision Quality of Life tool.
- intervention cost-benefit analysis

#### **4.7 Hypothesis framework**

PROSPER II is a superiority trial comparing glasses wear to non-wear. Analysis of the trial will entail calculation of treatment effect measures and confidence intervals to assess the difference between the two arms. Results from the statistical analysis will generally be presented by two-sided confidence intervals (CIs) with a confidence level of 95%. Superiority will be claimed if the two-sided p-value is less than 5% and the treatment estimate favours the use of glasses. If the lower limit is above 0, superiority of glasses-wear against non-wear can be concluded.

